## **9.4 Archiving**

All relevant study documents (trial master file), electronically derived data, the original CRFs and the final study report will be stored for at least 10 years at the ZKS Leipzig after trial completion.

At the study center, the investigator site file, the patient identification list, the signed informed consent forms, copies of CRFs, and the patient records will be stored for at least 10 years after the trial completion.

## **10 MONITORING OF THE CLINICAL TRIAL**

### **10.1 Access to source data**

Due to legal regulations for the protection of data quality and monitoring of the conduct of the study, the assessors are obligated to allow inspection of patient records (source data) to authorized third parties including monitors, auditors, and other authorized persons of the customer. These persons are obliged to secrecy.

### **10.2 Monitoring**

Monitoring will follow ICH-GCP guidelines and includes one initiation visit, one interim visit, and one close-out visit. For all patients, the informed consent documents will be checked. In addition, source data verification of the key data will be performed in a random sample of a portion of the patients. Monitoring will follow the ZKS SOPs.

### **10.3 Independent monitoring of the study**

Because of the small scope of this study, an independent Data Monitoring and Safety Committee (DMSC) was not deemed to be necessary. In case that a patient shows increased psychological distress during treatment, a clinical psychologist from the IFB Outpatient Unit will offer crisis intervention.

## **11 DATA SAFETY AND CONFIDENTIALITY**

In the context of the study, personal data of the patient including information about the treatment and course of disorder are assessed. These data are saved electronically and analyzed in a pseudonymized format (i.e., without explicit reference to the patient name) using an identification number.

Because it is necessary to contact patients directly, the name and address/telephone number of the patient are documented and saved after gathering written informed consent of the patient. These data are stored separately from the study data. Inference can be made using the patient identification number.

Data entry and processing take place at the ZKS Leipzig where a security concept guarantees protection against unauthorized access and data loss. In addition, the ZKS Leipzig is responsible for keeping the legal requirements of data protection. Study data are protected from unauthorized access and only study personal are allowed to access the data. The study personnel is obliged to secrecy.

In case that a patient withdraws informed consent, it will be checked whether the saved data are still required. Data that will not be required anymore will immediately be deleted. All assessed data will be deleted after the study objective was achieved/after finishing associated projects, or by 10 years, if not legal, statutory, or contractual periods of retention conflict.

### **Declaration of data protection**

Regarding data entry, processing, and analysis, which take place at the ZKS Leipzig, University of Leipzig, all legal regulations of data protection will be met. Study data are protected from unauthorized access and only study personal are allowed to access the data. The study personnel is obliged to secrecy.

## **12 ADMINISTRATIVE REGULATIONS**

### **12.1 Study conduct according to the study protocol**

The proposed clinical trial will be planned, conducted, and analyzed according to the requirements of the ICH-GCP and legal regulations.

Violations against the study protocol include all deviations from instructions and procedures as described in the study protocol. These are:

- Missing assessments/visits or malapropos assessments/visits, for example, not meeting the number of minimum treatment sessions
- Lack of compliance
- Intake of forbidden medication
- Screening failure (patient was randomized erroneously, i.e., inclusion criteria were not met or exclusion criterion was present)
- Concurrent psychotherapy (inpatient treatment lasting > 1 week or > 2 outpatient appointments for crisis intervention)
- Inpatient treatment due to other reasons lasting > 2 weeks

After a patient was included in the study, the assessor bears responsibility for avoiding protocol violations to retain the patient in the study.

Serious violations from the study protocol will immediately be reported to the principal investigator. All violations from the study protocol will be documented and discussed with the responsible biometrician prior to analysis.

The assessor has to make sure that all data were documented according to the study protocol. Small deviations cannot be avoided in everyday working life, but must be documented well grounded.

## 12.2 Funding and insurance

The study is funded by the German Federal Ministry of Education and Research (grant 01EO1501).

A patient insurance is not proposed as there is no use of medication or medical products. Instead, the trial includes a neuropsychological intervention for which patient and travel accident insurances are not necessary.

## 12.3 Publication agreement and registration

This trial is to be published in internationally accepted journals. The PI, [name], will make any effort for publishing the results of the study, independent from the direction of the study outcome.

[name]. [name] will be the first author. As co-authors, psychological or medical staff of the working group Behavioral Medicine, the University Medical Center Leipzig, cooperating partners, and the biometrician of the IFB data center will be considered, following established guidelines for authorship.

The authors are obliged to cite the IFB AdiposityDiseases. For institutional assignment, authors should use "University of Leipzig Medical Center, IFB AdiposityDiseases".

In all publications the BMBF must be acknowledged as follows:

"The study was funded by the German Federal Ministry of Education and Research (grant 01EO1501)."

Similarly, the funding institution and the IFB AdiposityDiseases must be mentioned for citable abstracts. On posters, the logos of the IFB AdiposityDiseases and the BMBF must be used in addition.

The study will be registered in a public study register, for example, the German Clinical Trials Register (DRKS), prior to the start of recruitment.

## 16 APPENDIX

### 16.1 Definitions

American Psychiatric Association (APA). Diagnostic and Statistical Manual of Mental Disorders, 5th ed.; DSM-5. Washington, DC: APA, 2013.

### Binge-Eating Disorder

#### Diagnostic Criteria

307.51 (F50.8)

- A. Recurrent episodes of binge eating. An episode of binge eating is characterized by both of the following:
  1. Eating, in a discrete period of time (e.g., within any 2-hour period), an amount of food that is definitely larger than what most people would eat in a similar period of time under similar circumstances.
  2. A sense of lack of control over eating during the episode (e.g., a feeling that one cannot stop eating or control what or how much one is eating).
- B. The binge-eating episodes are associated with three (or more) of the following:
  1. Eating much more rapidly than normal.
  2. Eating until feeling uncomfortably full.
  3. Eating large amounts of food when not feeling physically hungry.
  4. Eating alone because of feeling embarrassed by how much one is eating.
  5. Feeling disgusted with oneself, depressed, or very guilty afterward.
- C. Marked distress regarding binge eating is present.
- D. The binge eating occurs, on average, at least once a week for 3 months.
- E. The binge eating is not associated with the recurrent use of inappropriate compensatory behavior as in bulimia nervosa and does not occur exclusively during the course of bulimia nervosa or anorexia nervosa.

### Other Specified Feeding or Eating Disorder

307.59 (F50.8)

This category applies to presentations in which symptoms characteristic of a feeding and eating disorder that cause clinically significant distress or impairment in social, occupational, or other important areas of functioning predominate but do not meet the full criteria for any of the disorders in the feeding and eating disorders diagnostic class. The other specified feeding or eating disorder category is used in situations in which the clinician chooses to communicate the specific reason that the presentation does not meet the criteria for any specific feeding and eating disorder. This is done by recording "other specified feeding or eating disorder" followed by the specific reason (e.g., "bulimia nervosa of low frequency").

Examples of presentations that can be specified using the "other specified" designation include the following:

3. **Binge-eating disorder (of low frequency and/or limited duration):** All of the criteria for binge-eating disorder are met, except that the binge eating occurs, on average, less than once a week and/or for less than 3 months.

## 16.2 Abbreviations

ADHD	attention deficit-/hyperactivity disorder
AE	adverse event
BED	binge-eating disorder
BMI	body mass index
BWL	behavioral weight loss
DSM-5	Diagnostic and Statistical Manual of Mental Disorders, 5 th edition
EEG	electroencephalography
EK	ethical commission
FAS	full analysis set
fMRI	functional magnetic resonance imaging
fNIRS	functional near infrared spectroscopy
GCP	good clinical practice
GCP-V	GCP-regulation
ICH	International Conference on Harmonisation
IFB	Integrated Research and Treatment Center AdiposityDiseases
OBE	objective binge-eating episode
PET	Positron Emission Tomography
PIL	patient identification list
PPS	per-protocol set
ROI	region of interest
SAE	serious adverse event
SOP	standard operating procedure
ZKS Leipzig	Zentrum für Klinische Studien Leipzig (Clinical Trial Centre Leipzig)
WL	waiting list
WLM	weight loss maintenance

## 1 Introduction

The purpose of this document is to provide a detailed elaboration of the statistical analysis described in the protocol, including detailed procedures for the confirmatory analysis of the primary and secondary endpoints and other variables.

The SAP is based on the planned analysis specification as written in the study protocol, section 7 “Biometric Aspects of the Study”. All data will be analysed and reported in accordance with a recently published checklist (CRED-nf checklist; Ros et al., 2020). The table can be found in appendix 6.4.

The software package R Version 3.6.1 or higher will be used for statistical analyses. To reproduce online analysis, Turbo-Satori (TSI) 1.0.0. (BrainInnovation B.V., Maastricht, the Netherlands; Lührs & Göbel, 2017) will be used. Offline analyses of fNIRS data will be carried out with MATLAB R2018b using the Brain AnalyzIR Toolbox (Santosa et al. 2018); see Item 4e of the CRED-nf checklist).

Database variables are denoted by **this font and colour**.

## 2 Endpoints and further variables

### 2.1 Primary endpoint

The number of objective binge-eating episodes (OBEs) over the past 28 days at post-assessment (T1, **visit\_label=T1** for the intervention groups) or after the waiting period (**visit\_label=T0WL** for the waitlist control group; Item 6a of the CRED-nf checklist). OBEs are derived from the well-established Eating Disorder Examination interview (**oepism1**) and will be compared between groups, correcting for the baseline value (**visit\_label=T0**). The trial protocol stipulated that the number of OBEs over the past 14 days would be analysed. Based on the standard EDE instrument and the accepted endpoint, the value over the past 28 days will be used (Item 6a of the CRED-nf checklist).

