### 7.2 Endpoints

#### 7.2.1 Primary endpoint

The number of objective binge-eating episodes (OBEs) over the past 14 days at post-treatment (t1), derived from the well-established Eating Disorder Examination interview, **will be compared between groups, correcting for the baseline value**. OBEs are consistently reported as the primary outcome measure in BED treatment trials.

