### 7.3 Statistical description of the trial hypothesis

This clinical trial evaluates whether neurofeedback results in fewer objective binge-eating episodes after

end of treatment (i.e., 2 months after randomization) than a delayed treatment group. Furthermore fNIRS neurofeedback, EEG neurofeedback, and delayed treatment will be compared.

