## b) Eating disorder psychopathology

- Number of OBEs (T0, T2) defined as for the primary endpoint
- Abstinence from objective binge eating (T1-T2) meaning `oepism1==0`
- Remission (T1-T2), (remission means `bedfull= bedlfrq = bedlimdu = nein`), partial remission (T1-T2), defined as change from `bedfull` to `bedlfrq` or `bedlimdu` – only those with `bedfull` at T0 will be included in the endpoint analysis of partial remission. All data will be included in descriptive statistics.
- Eating disorder psychopathology (EDE-Q) (T0-T2): the global score and the four subscale-scores (restraint, weight concern, shape concern, eating concern) will be used

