### 4.1 Primary endpoint

The primary endpoint, the number of OBEs at post-assessment or post-waiting, will be analysed using ANCOVA with OBEs as the dependent variable, OBEs at T0 as a covariate as well as the stratification criteria (`strabmi`, `stralsex`, `strawei`). The code for this test will have the structure

```
anova(lm(OBE_FU ~ OBE_T0 + STRABMI + STRASEX + STRAWEI + ARMS)).
```

The variables OBE\_FU and OBE\_T0 will be shifted by the mean of OBE at T0 so that the intercept in the model reflects change in time. A closed-testing procedure will be used, meaning

---

 The planned dates are as follows: session 1/2 (week 1), session 3/4 (week 2), session 5/6 (week 3), session 7/8 (week 4), session 9 (week 5), session 10 (week 6), session 11 (week 7), session 12 (week 8),

that the initial comparison will be between the two intervention groups combined and the waiting group and the three pair-wise tests (fNIRS vs. wait control group, EEG vs. wait control group and fNIRS vs. EEG group) will be performed without adjustment if the global test is significant. If the global test is not significant, estimates and confidence intervals will still be provided for the contrasts in OBE, but no formal statistical test will be carried out. Estimates will be taken from the linear model and a Wald confidence interval will be used. Moreover, secondarily, the analogous analysis with effect size will be performed.

Missing data will be treated with multiple imputation using the R package “mice” (van Buuren and Groothuis-Oudshoorn 2011). The imputation variables will include the answer to the question “In how many of the situations in which you ate too did you feel you had lost control of your eating behaviour” (pre72). Sex, BMI and the stratification variable participation in a weight-loss programme will also be used. Fifty imputations will be performed.

To test the robustness of the results, the primary analysis will be repeated without imputation and pessimistic and optimistic scenarios will be considered.

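### SAP 2.1 changes the primary endpoint from a 14-day to a 28-day OBE count, keeps no analysis of the protocol's count, and does not say whether the change was made blind to outcome data

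*SAP*

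**What the plan says.** Protocol 7.2.1 defines the primary endpoint as "The number of objective binge-eating episodes (OBEs) over the past 14 days at post-treatment (t1"), taken from the Eating Disorder Examination (EDE) interview and corrected for baseline. The synopsis and Protocol 1.2.1 and 2.1 say the same.

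SAP 2.1 defines it as "The number of objective binge-eating episodes (OBEs) over the past 28 days at post-assessment", or after the waiting period (T0WL) in the control arm. It acknowledges the departure: "The trial protocol stipulated that the number of OBEs over the past 14 days would be analysed". Its reason is: "Based on the standard EDE instrument and the accepted endpoint, the value over the past 28 days will be used".

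For robustness, SAP 4.1 says "the primary analysis will be repeated without imputation and pessimistic and optimistic scenarios will be considered". No 14-day analysis is listed there. Among the secondary endpoints in SAP 2.2 the new window carries over: "Number of OBEs (T0, T2) defined as for the primary endpoint". Abstinence uses the same database variable.

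**The concern.** The primary endpoint carries the trial's one confirmatory test. When its definition changes after the protocol, a reader needs to know whether those who made the change could have seen outcome data by arm, and what the protocol-defined endpoint would have shown. The visible SAP text gives neither.

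The SAP was not written before the trial ran. SAP 3.1 reports that three patients had been replaced, builds SARS-CoV-2 losses into the full analysis set, and records that psychological treatment during participation did not occur. SAP 2.2 speaks of the waiting group's later intervention in the past tense. The stated reason also points to nothing new: Protocol 7.2.1 named the EDE, and the standing of OBEs as the usual primary outcome, in the same paragraph that set 14 days.

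The window is not a formality. It decides which weeks of an eight-week treatment count towards the outcome.

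**Working it through.** The plan gives no figure that compares the two windows, so there is none to reproduce. The check has two parts.

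**1. What each window covers.** Inputs: 12 sessions over 8 weeks (Protocol 1.2.1); t1 at week 8, with up to 2 further weeks allowed (Protocol 5.4); and the planned calendar in the footnote to SAP 4.1, with two sessions a week in weeks 1-4 and then "session 9 (week 5), session 10 (week 6), session 11 (week 7), session 12 (week 8").

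| T1 visit | Window | Weeks covered | Sessions inside | Sessions before |
|---|---|---|---|---|
| Week 8 | 28 days | 5-8 | 4 | 8 |
| Week 8 | 14 days | 7-8 | 2 | 10 |
| Week 10, treatment ended week 8 | 28 days | 7-10 | 2 | 10 |
| Week 10, treatment ended week 8 | 14 days | 9-10 | 0 | 12 |

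Protocol 7.3 words the hypothesis as fewer episodes after "end of treatment (i.e., 2 months after randomization) than a delayed treatment group". At a week-8 visit both windows lie within treatment. The contrast is between earlier and later treatment weeks, and it moves towards post-treatment time as the visit slips into the allowance. In the waiting arm, 28 days at week 8 is the second half of the waiting period.

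**2. Which way the result could move.** None of the following assumptions is in the documents. The effect on the weekly OBE rate grows linearly from zero at week 0 to a 40% reduction at week 8. Counts are gamma-Poisson with a stable patient-level rate, m = 0.5 to 3.5 episodes per week, and between-patient coefficient of variation c = 0.3 to 1.0. T1 is at week 8 and baseline adjustment is ignored. The group sizes are 42 and 21, from Protocol 7.4.4.

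- Share of the week-8 effect captured: 28 days, (4/8 + 8/8)/2 = 0.75; 14 days, (6/8 + 8/8)/2 = 0.875.
- Control mean μ = m × weeks in the window; treated mean μ_t = μ(1 − 0.4 × share); variance of a count with mean x is x + (cx)².
- Standardised effect d = (μ − μ_t)/√[(42·var_t + 21·var_c)/63].

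Low rate, similar patients (m = 0.5, c = 0.3):
- 14 days: μ = 1, μ_t = 0.65, variances 1.09 and 0.688, d = 0.35/0.907 = 0.386.
- 28 days: μ = 2, μ_t = 1.4, variances 2.36 and 1.576, d = 0.6/1.356 = 0.443.
- Ratio 28-day to 14-day: 1.15. With m = 1 it is 0.589/0.528 = 1.12.

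High rate, heterogeneous patients (m = 3.5, c = 1.0):
- 14 days: μ = 7, μ_t = 4.55, variances 56 and 25.25, d = 2.45/5.958 = 0.411.
- 28 days: μ = 14, μ_t = 9.8, variances 210 and 105.84, d = 4.2/11.856 = 0.354.
- Ratio: 0.86.

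The longer window takes in less-treated weeks but reduces count noise. Which dominates depends on rates and heterogeneity that the documents do not give.

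**The case against.** The sponsor has a good case. The SAP quotes the protocol's rule, departs from it openly and gives a reason, which cannot be tested without the EDE manual. The facts known when the SAP was written are conduct facts, not OBE results by arm. SAP 4.5 says no interim analysis was planned or performed, Protocol 3.2 has assessors blind to randomisation, and Protocol 7.8 puts the final analysis after database lock. The SAP's front pages were not in the text reviewed, so a date or version history may stand there.

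The longer count also has a measurement rationale. Patients with BED of low frequency are eligible (Protocol 4.1). At less than one episode a week they average fewer than 2 episodes in 14 days and fewer than 4 in 28, so the shorter count is coarse.

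All of this stands. It rules out two inferences a reader might draw: that the window was chosen for its result, and that 14 days must be restored as primary. The first has no support in the documents; the second is a trade-off the sponsor may settle either way. But none of it says whether those who chose the window were blind to OBE data, and none of it gives the reader the result for the endpoint the protocol specified.

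**Conclusion.** The point holds as one of transparency and robustness. The primary endpoint was changed in a document written after conduct events were known, the visible text is silent on blinding to OBE data, and no analysis of the protocol's endpoint remains. The windows differ in exposure by the session counts shown above, on the planned calendar.

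A reader might go further in two ways. One is to claim that the 28-day window costs power. That follows only if the standardised SD is held fixed; once count noise is modelled, the ratio of standardised effects runs from about 0.86 to 1.15. The effect size of 0.55 in Protocol 7.4.4 is also not tied to any recall window. The other is to claim that the 28-day window alone conflicts with a hypothesis about the period after treatment. At a week-8 visit the 14-day window contains sessions 11 and 12, so it has the same limitation to a lesser degree.

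Because the two results may differ in either direction, both should be shown.

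**What to change.** Add to SAP 4.1 a prespecified sensitivity analysis: the 14-day OBE count at T1/T0WL, adjusted for the 14-day count at T0, with the same ANCOVA, contrasts and imputation. Report it beside the 28-day result. Expressing both per week would make the estimates comparable. The 28-day count can remain primary.

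In SAP 2.1, state when the window was changed and whether that was before anyone involved had seen OBE data by arm. Report it as a change to the protocol's primary endpoint.

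If the 14-day count was not recorded in the EDE interview, say so and report that as a protocol deviation. The SAP names only one OBE variable, so this cannot be judged from the documents. The weekly OBE records cannot fill the gap: in the delayed-treatment arm they cover weeks 9-15 (Protocol 5.4), after the T0WL assessment is due.

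The cost is a few lines of SAP text and one further run of existing code, provided the 14-day data exist. SAP 4.3 already announces a next version of the SAP, which could carry the addition. The downside is one more analysis to report; labelled as sensitivity, it leaves the confirmatory test unchanged.

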### 2.2 Secondary endpoints (Item 6a of the CRED-nf checklist)

Unless otherwise indicated, the scores from questionnaires are calculated using the “qscorer” package from [name] (see appendix for code). Comparisons between all three groups are foreseen at T0 (baseline) and T1/T0WL. After T0WL, the WL control group received an fNIRS intervention. Hence, T2 can only be used to estimate changes within a group and between the two intervention groups.

#### a) Feasibility (between T0-T1)

- Recruitment: a graphical depiction of recruitment will be provided along with the mean recruitment rate
- Attrition: The number of treatment sessions attended in the intervention groups (based on **exdat**) will be provided by randomization arm and taking dropout due to SARS-CoV-2 into account
- Assessment completion: Valid OBEs at T1 will be counted as “assessment completion”
- Compliance: Therapist’s evaluation at T1 on personal effort, general motivation, and treatment success (**eff3**, **moti4**, **succ5**), scale between 0-5
- Patients’ program evaluation: Patient’s response in the last session attended to question 3 (**PRE31**, **PRE32**, **PRE33**): “How helpful was the neurofeedback training until now in your opinion (a) in general, (b) as it pertains to your eating behaviour,(c) in order to relax”?, scale between 0-6

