## Protocol synopsis

Title of the study:	Near Infrared Spectroscopy Neurofeedback for Binge-Eating Disorder (NIRSBED)
Abbreviation of the study:	NIRSBED
Condition:	Binge-eating disorder (BED)
Primary objective of the study:	Efficacy of functional near infrared spectroscopy (fNIRS) neurofeedback in the treatment of adult binge-eating disorder
Secondary objective of the study:	Feasibility of fNIRS neurofeedback including recruitment, attrition, assessment completion, patients' program evaluation, and efficacy on eating disorder psychopathology, executive functioning, weight loss maintenance behavior, and mental and physical health  Determining the specificity of efficacy of fNIRS neurofeedback via comparison with active and inactive control conditions
Study design:	Single-center, assessor-blinded, randomized-controlled, three -armed, feasibility study
Study population:	
Inclusion criteria:
 
 
- Ages <math>\geq</math> 18 years
 
- Full syndrome binge-eating disorder (BED) or BED of low frequency and/or limited duration according to DSM-5
 
- BMI: 25.0 - 45.0 kg/m^2
 
- Written informed consent
 
- Sufficient German language skills
 
- Feasible commute to the IFB Research Unit
 
 
Exclusion criteria:
 
 
- Serious somatic conditions (e.g., neurological disorders, stroke, head injury)
 
- Serious mental disorders (e.g., psychotic disorder, suicidality, substance use disorder, ADHD, developmental or intellectual disability)
 
- Impediment in hearing, vision, or language with an effect on testing
 
- Previous or planned bariatric surgery
 
- Use of medication that impacts weight or executive functioning (e.g., antipsychotics)
 
- Ongoing psychotherapy
 
- Pregnancy or lactation
 

Sample size:	N = 78, n = 26 per study arm
Therapy:	
Experimental intervention:
 
12 sessions (60 min) over 8 weeks of fNIRS neurofeedback treatment focusing on food-related self-regulation for improving binge eating and associated psychopathology, executive functions, weight loss maintenance behavior, and mental and physical health.

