## 1.2 Rationale

### 1.2.1 Hypotheses and experimental aspects of the clinical trial

Given the need to further improve treatment outcome for BED, new treatments should address underlying neurobehavioral difficulties such as low inhibitory control. Based on the initial evidence on neurofeedback described above, investigation of fNIRS neurofeedback in adults with BED is a logical next step of research. Improved self-regulation likely has an impact on weight management; in fact, binge eating is a negative prognostic indicator for long-term WLM. Thus, the goal of this randomized-controlled trial (RCT) is to evaluate the feasibility and efficacy of fNIRS neurofeedback in patients with BED and overweight or obesity. It is hypothesized that fNIRS neurofeedback will be feasible and estimates regarding efficacy will be better than for delayed treatment control. The number of objective binge-eating episodes (OBEs) over the past 14 days at post-treatment (t1), derived from the Eating Disorder Examination, **will be compared between groups, correcting for the baseline value.** OBEs are consistently reported as the primary outcome measure in BED treatment trials. In order to address the specific mechanisms of action, fNIRS neurofeedback will further be compared to EEG neurofeedback. As BED and the associated comorbidities increase direct and indirect societal costs beyond those of obesity alone, fNIRS neurofeedback has the potential to produce a reduction of these costs. In Germany and internationally, evaluations of fNIRS treatment approaches in BED are lacking. It is thus a clinical and research priority to examine the feasibility and efficacy of fNIRS neurofeedback for adults with BED.

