#### 7.2.2 Secondary endpoints

- (a) Feasibility (between t0-t1): Recruitment, attrition, assessment completion, compliance, patients' program evaluation
- (b) Number of OBEs (t0, t2), remission from objective binge eating (EDE) (t0-t2), eating disorder psychopathology (EDE-Q) (t0-t2)
- (c) Neuropsychological and neurophysiological outcomes (t0, t1): e.g., inhibition (Go/NoGo task)
- (d) Weight management-related behaviors (t0-t2): e.g., self-efficacy (GSES)
- (e) Mental health (t0-t2): e.g., depressive symptoms (PHQ-D)
- (f) Physical health (t0-t2): e.g., body mass index (kg/m^2)

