## 3 General analysis definitions

### 3.1 Analysis populations

Analysis of the primary and secondary outcomes are based on the full analysis set (FAS). Note that patients fulfilling the criterion for abstinence at T0 will not be included in the analysis for this endpoint. Further, the analysis of the primary outcome will be performed in the per-protocol set (PPS) to evaluate the treatment effect for patients with good protocol adherence, if FAS and PPS comprise a sufficiently different set of patients. Analysis of the fNIRS data will be performed in the fNIRS data set.

The FAS includes all randomized patients unless purely technical issues precluded the fNIRS measurements. In particular, three patients had to be replaced because of the aforementioned technical issues with fNIRS. Patients who could not complete the intervention due to the SARS-CoV-2 situation will be retained in the FAS if they completed at least 5 sessions and provided OBE data at T1. In control patients, those who could not attend T0WL due to SARS-CoV-2 will not be retained in the FAS.

The PPS includes all patients of the FAS without serious violations of the study protocol. The following protocol violations are classified as serious:

- Violation of at least one inclusion or exclusion criterion

- Treatment was not conducted as mandated, that is
  - Temporal delay of last attended treatment session by 4 weeks relative to the planned date, `exdat`, (based on the date of the first treatment session). Note that consideration of a maximum of two weeks' delay in each session as originally foreseen was not considered feasible.
  - Absence of more than 6 of the planned 12 treatment sessions (based on `meet`)
- Use of forbidden medication
- Psychological treatment during study participation (was not the case, otherwise it would be documented in the "comments")

The fNIRS/EEG data set includes all patients from the fNIRS/EEG group of the FAS who provided data for more than a single neurofeedback session. Participants with fewer sessions are excluded from the analyses, because the definition of neurofeedback *training* does not apply for these participants and there is no information on between-session variability.

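### Feasibility rates fall under an analysis set that omits the three patients replaced for fNIRS technical problems, and no feasibility item counts technical failure

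*SAP*

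**What the plan says.** Feasibility is a declared aim. The protocol calls the trial a feasibility study (synopsis and section 3.1). The synopsis lists "Feasibility of fNIRS neurofeedback including recruitment, attrition, assessment completion" among the secondary objectives, and section 1.2.1 states: "It is hypothesized that fNIRS neurofeedback will be feasible".

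The components are fixed in protocol 7.2.2 ("Recruitment, attrition, assessment completion, compliance", then program evaluation) and defined in SAP 2.2 a). Attrition is "The number of treatment sessions attended in the intervention groups", reported by randomisation arm. Assessment completion is a valid count of objective binge-eating episodes (OBEs) at T1. Compliance is a therapist rating at T1. Program evaluation is the patient's answer in the last session attended.

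SAP 2.2 a) names no analysis set, so the general rule in SAP 3.1 applies: "Analysis of the primary and secondary outcomes are based on the full analysis set (FAS"). The same section continues: "The FAS includes all randomized patients unless purely technical issues precluded the fNIRS measurements", and reports that "three patients had to be replaced because of the aforementioned technical issues with fNIRS".

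Protocol 7.5.1 defines the FAS as every randomised patient, with no technical exception. SAP section 4 plans a CONSORT flowchart covering all randomised patients, with their analysis-set membership and details of treatment and assessment completion.

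**The concern.** Excluding a patient because the device could not be used may be arguable for an efficacy comparison. For feasibility it removes part of what is being measured: whether the treatment can be delivered to those assigned to it. The FAS exception is written for fNIRS only. Attrition is reported by arm, so fNIRS and EEG would be counted under different rules, and the difference can favour the experimental device.

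No other planned output turns these patients into a feasibility result:

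- The fNIRS and EEG data sets are drawn from the FAS and also require more than one session (SAP 3.1).
- The outlier counts in SAP 4.3 concern data that were recorded.
- The qualitative analysis in protocol 7.5.2 covers recruitment and patient commitment.
- The device-deficiency text in protocol 6.2 concerns incident reporting and names only the EEG manufacturer.

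At stake is whether a feasibility study's own feasibility figures include the one fNIRS delivery problem that its SAP documents.

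**Working it through.** **Inputs.** Three patients replaced for technical reasons, arm not given (SAP 3.1). 26 planned per arm, 78 in total (protocol synopsis). 63 expected to be analysed, 21 of them in the waiting group (protocol 7.4.4). Planning drop-out about 20% (protocol 7.4.3).

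**The plan's own figure.** The plan gives no technical-failure rate, only the count of three. Its drop-out allowance can be recovered: (78 − 63)/78 = 15/78 = 19.2%, or 5 of 26 per arm.

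**Technical-failure rate.** Assume each replacement refilled its arm to exactly 26. With k of the three randomised to immediate fNIRS, the rate is k/(26 + k):

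| k | Rate in the fNIRS arm |
|---|---|
| 0 | 0/26 = 0% |
| 1 | 1/27 = 3.7% |
| 2 | 2/28 = 7.1% |
| 3 | 3/29 = 10.3% |

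If all three came from the two arms offered fNIRS (immediate and delayed), the rate is 3/(26 + 26 + 3) = 3/55 = 5.5%.

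**Wilson 95% intervals.** Limits are [p + z²/2n ± z√(p(1 − p)/n + z²/4n²)] / (1 + z²/n), with z = 1.96.

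- 3/29: (0.1034 + 0.0662 ± 0.1291)/1.1325, giving 3.6% to 26.4%.
- 3/55: (0.0545 + 0.0349 ± 0.0694)/1.0698, giving 1.9% to 14.9%.

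**Effect on attrition (illustration).** Suppose 5 of 26 fNIRS patients stop treatment, as the planning allowance implies. The FAS gives 5/26 = 19.2% non-completion. Restoring k technical failures gives (5 + k)/(26 + k): 6/27 = 22.2%, 7/28 = 25.0% or 8/29 = 27.6%.

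**Effect on assessment completion (illustration).** With 21 of 26 assessed, the FAS gives 80.8%. If three technical failures belong to this arm and none was interviewed at T1, the rate is 21/29 = 72.4%. If all three were interviewed, it is 24/29 = 82.8%. The OBE count comes from an interview that does not need the device, and the documents do not say whether these patients were followed.

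**Direction.** Patients whose fNIRS measurement was precluded would be expected to have attended fewer fNIRS sessions than the rest. On that basis, leaving them out either does nothing to fNIRS attrition (k = 0) or makes it look better. Assessment completion moves the same way unless these patients still gave T1 data.

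**The case against.** The strongest reply is that nothing is hidden. SAP 3.1 states the number and the reason, and the flowchart in SAP section 4 covers all randomised patients and gives completion details. That stands: the patients are traceable. What is missing is a feasibility rate with numerator, denominator and interval that includes them. A reader might infer that three failures are being reported as none. The documents do not support that; the three are disclosed but not counted in the feasibility rates.

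Second, the FAS is inferred for feasibility, because SAP 2.2 a) names no set. The inference follows from the rule for secondary outcomes, but it cannot sensibly govern recruitment. Compliance and program evaluation need treatment exposure, so these patients may have no values under any set. Only attrition and assessment completion could plausibly change.

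Third, the arm is unknown. Delayed-treatment patients also receive fNIRS, but after the waiting period. If all three were in that arm, attrition and completion in the immediate fNIRS arm would not change. This stands, and it is why the range starts at 0%.

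Fourth, the nature of the problem is not described. It may have been an equipment outage or a signal problem in particular patients. Reading it as an inability to obtain a usable signal from those patients goes beyond the text.

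Fifth, the SAP keeps the five components that the protocol specified, and neither document sets a feasibility threshold. No pass or fail conclusion can therefore change.

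**Conclusion.** The point holds as a possible one-sided bias and a reporting gap. The SAP narrows the protocol's FAS for an fNIRS-specific reason, applies that set to feasibility through its general rule, and has no item for technical failure.

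The size is 0% to 10.3% technical failure in the fNIRS arm, or 5.5% over both arms offered fNIRS. Both figures assume replacement up to 26 per arm; the 5.5% also assumes that all three came from those two arms. The intervals are wide because the count is three.

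It is tempting to conclude that fNIRS will definitely appear more feasible than it was. The documents do not support that without the arm of the three patients and, for assessment completion, whether they were followed to T1. This is a cheap improvement to the plan, and it does not depend on whether the exclusion is acceptable for the OBE analysis.

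**What to change.** In SAP 2.2 a):

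- State that attrition and assessment completion are calculated on all randomised patients, replaced ones included, by arm.
- Add one row for technical failure, by device and arm, with a Wilson interval. SAP 4.2.1 already uses that interval for proportions.
- Show these patients within total attrition as a cause separate from patient drop-out. Merging the two would mix device reliability with patient retention.
- State the arm and timing of the three replacements.

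Using all randomised patients here also avoids a related condition in SAP 3.1: intervention patients stopped by SARS-CoV-2 stay in the FAS only if they have at least 5 sessions and OBE data at T1, which are the things that attrition and assessment completion measure.

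The cost is a few sentences and one table row. The efficacy analysis is untouched. The stated feasibility of fNIRS may become slightly less favourable.
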